## 6.2 BLINDING

This study will be single blinded (patients only). The primary end point is an objective physiological parameter which cannot be influenced by any observer bias.

## 7. METHODS: DATA COLLECTION, MANAGEMENT, AND ANALYSIS

#### 7.1 Data collection methods

Data will be collected from patient notes (pre-operative assessment booklet, anaesthetic chart, operative note, notes made post-operatively) and the ERP Database. The research team will perform the blood sampling and record the measured results as described and collect the VAS scores.

#### PRE-OPERATIVE ASSESSMENT CLINIC

- Fasting POCT blood glucose to confirm eligibility (or use of previous HbA1C result if available)
- Baseline demographics Pre-op Blue Document
- Height and weight Pre-op Blue Document
- Mid Upper Arm Circumference (MUAC)
- ASA score ERP Database
- Co-morbidities Pre-op Blue Document
- Baseline PQRS score questionnaire
- Baseline hand grip strength measurement
- Baseline fasted blood samples (to be combined with routine blood sampling).
  - Fasting Glucose
  - Fasting Insulin (3 sample to be taken at 5 minute intervals)
  - Cortisol

- o CRP
- HbA1c (if not recently measured)

#### **OPERATIVE DAY PRE-SURGERY**

- Confirm allocated drinks consumed as per instructions & document
- · Thirst and hunger sensation VAS score
- Blood samples on morning of surgery fasted (before consuming the intervention) if not done in POAC.
  - Fasting Glucose
  - Fasting Insulin (3 sample to be taken at 5 minute intervals)
  - Cortisol
  - o CRP
  - HbA1c (if not recently measured)
- Duration surgery (obtained from Theatreman system)
- Volume of blood loss
- Description of operation and type of primary analgesia obtained from Theatreman system or ERP Database
- Calories consumed

## POST-OPERATIVE DATA COLLECTION

- POSSUM score from ERP Database
- Blood samples:
  - Fasting insulin (3 samples to be taken at 5 minute intervals and glucose on the morning of POD 1, 2 and 3
  - Cortisol (at end of operation and at 24 hours)
  - o CRP (POD 1 and 3)
- PQRS score Theatre Recovery, POD 3 and POD 7.
- PONV and Thirst and hunger sensation VAS scores on POD 1.
- POMS score on POD 2 and 5
- Hand grip strength measurement twice daily on POD 1, 2 & 3 and then alternate days until discharge
- Calories intake POD1 and POD2
- Ambulation time (minutes) POD1 and POD2
- MUAC POD5 or Day of Discharge if earlier
- Adverse Events up to end POD 1.
- Date and time reached surgical fitness for discharge and actual discharge obtained from ERP Database

## 7.2 DATA MANAGEMENT

Identifiable data including full name, date of birth and hospital number will be required by the research team for identification purposes during the post-operative phase. All patient confidentiality will be ensured. The trial team will not disclose or reproduce any information by which patients could be identified. All patient data collected will be entered on to a password-protected Microsoft Excell Spreadsheet. The CI will ultimately be responsible for data collection, quality and recording and handling however data collection will be delegated to the Clinical Research Anaesthetic Fellow and ERP Data Clerk. The R&D Quality Manager will undertake monitoring to assess data quality. A separate and secure log will be kept with consent form and identifiers to allow patient follow up. During the conduct of the trial all electronic patient data will be encrypted and all trial documents stored securely at East Lancashire Hospitals NHS Trust. Following completion of the trial all non-essential confidential documents will be destroyed and essential documents (paper and electronic) will be archived and retained securely for five years in accordance with ICH GCP guidelines. Essential documents are

those which enable both the conduct of the trial and the quality of the data produced to be evaluated and to show whether the unit complied with the principles of ICH GCP and other applicable regulatory requirements.

All archived documents should be available for inspection by appropriate authorities upon request.

#### **END OF TRIAL**

The end of the trial will be when the final patient has been discharged from hospital, at which point the 'declaration of end of trial' form will be submitted to the REC, as required.

#### 7.3 STATISTICAL METHODS

#### STATISTICAL METHODS FOR ANALYSING PRIMARY AND SECONDARY OUTCOMES

Baseline demographic and clinical variables will be reported for the two groups using summary statistics. Categorical variables will be reported using frequencies and percentages. Quantitative variables will be reported using either the mean and standard deviation or the median and interquartile range depending on the skewness of the data

In terms of the primary outcome, the mean difference in change of insulin resistance from baseline to POD 1 will be compared using either the Independent Samples T-Test or Mann-Whitney U Test. This will depend on the skewness of the data distribution.

Between-group comparisons of quantitative secondary outcomes including change of insulin resistance from baseline to POD 3, the PQRS score and time to surgical fitness will made using either the Independent Samples T-Test or Mann-Whitney U Test, depending on the skewness of the distribution of the data. Categorical secondary outcomes will be compared between groups using the Chi-square test.

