#### 5.4 OUTCOMES

## PRIMARY OUTCOME

 Change in insulin resistance from baseline on POD 1 measured using a technique called HOMA (see Appendices), which utilises serial fasting blood glucose and insulin measurements.

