#### 5.6 Sample Size

The standard deviation for insulin resistance data was obtained from a previous study of pre-operative carbohydrate treatment in total hip replacement surgery (Soop 2001). Twenty patients in each group are needed based on 80% power for a two-sample t-test, detecting a minimal important difference of 15% in change of insulin resistance on the first postoperative day from baseline, with a standard deviation of 16% and a two-tailed significance level of 0.05. A minimal important difference of 25% was used in a previous study comparing pre-operative carbohydrate treatment with a placebo group for patients who had total hip replacement (Soop 2004) . In this study two carbohydrate drinks are being compared, PreLoad with Generation UCAN. Therefore, a smaller minimal important difference of 15% was deemed appropriate. This sample size calculation allows for 10% attrition.

\*\* Measured twice a day first three postoperative days then alternate days until discharge from hospital.

\*\*\*The baseline HOMA to be done on either of these 2 visits as long as the patient is fasted.

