## METHODS FOR ANY ADDITIONAL ANALYSES (EG, SUBGROUP AND ADJUSTED ANALYSES)

If differences are observed in baseline demographic and/or clinical variables prognostic of outcome, then the analysis of the primary and secondary outcomes will be adjusted for using regression-based analysis appropriate to the type of outcome variable. The trial statistician will describe details of sub-group analysis in the statistical analysis plan if possible.

DEFINITION OF ANALYSIS POPULATION RELATING TO PROTOCOL NON-ADHERENCE (E.G., AS RANDOMISED ANALYSIS), AND ANY STATISTICAL METHODS TO HANDLE MISSING DATA (EG, MULTIPLE IMPUTATION) All analysis will be performed according to the intention to treat principle. The primary analysis will be based only on data obtained; sensitivity analysis will explore sensitivity to assumptions around missing data and details will be included in the statistical analysis plan devised by the trial statistician.

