## CALCULATION OF INSULIN RESISTANCE

Insulin resistance will be calculated using the University of Oxford Diabetes Trial Unit HOMA calculator (freely available from https://www.dtu.ox.ac.uk/homacalculator/index.php). Although the Clamp method is considered the "gold standard" for assessing insulin sensitivity this is limited to small-scale intensive physiological investigations and not pragmatic for anything larger i.e. our proposed study.

The homeostatic model assessment (HOMA 1) of pancreatic  $\beta$ -cell function was first described by Matthews et al in 1985. This technique uses basal glucose and insulin or C-peptide concentrations to calculate  $\beta$ -cell function and insulin sensitivity. Insulin resistance is calculated as the inverse of sensitivity (%IR = 100/%IS).

The University of Oxford calculator is based upon the updated HOMA 2 computer model. This model is accurate across a range of insulin (1-2200pmol/l) and glucose (1-25mmol/l). This non-linear model is optimised to calculate insulin sensitivity from fasting glucose and insulin levels. This method is shown to correlate well with the 'gold standard' euglycaemic ( $R_s = 0.85$  to 0.88, p < 0.0001) and hyperglycaemic ( $R_s = 0.61$ , p < 0.01)

[figure not shown]
clamp methods of calculating insulin sensitivity and has been used as a measure of insulin resistance in over 500 publications to date.

The Clamp techniques reflect the stimulated state and the HOMA technique reflects the basal state. The Clamp allows differentiation between liver EGP and peripheral tissue (primarily skeletal muscle) glucose uptake regarding insulin sensitivity whereas HOMA does not differentiate between the sources of insulin resistance.

Fortunately this will not be an issue in our study as it has been shown by Soop et al that postoperative insulin resistance shifts from exclusively peripheral tissue insulin resistance, with a very minor role from the splanchnic tissues, in the first 24 hours, to a substantial role from liver EGP at the third postoperative day onwards. Therefore any insulin resistance measured in our study will be assumed to align with the respective tissues depending on the postoperative timing.

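### The primary comparison is defined as a mean difference, but the test, and any covariate adjustment, are to be chosen from the observed data instead of being fixed as one baseline-adjusted model

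*Protocol*

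**What the plan says.** The primary outcome in protocol section 5.4 is "Change in insulin resistance from baseline on POD 1 measured using a technique called HOMA". The HOMA appendix adds: "Insulin resistance is calculated as the inverse of sensitivity (%IR = 100/%IS".

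Section 7.3 states that "the mean difference in change of insulin resistance from baseline to POD 1 will be compared", and that the groups will be "compared using either the Independent Samples T-Test or Mann-Whitney U Test. This will depend on the skewness of the data distribution". It gives no skewness cut-off, no diagnostic, no default test and no transformation.

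The paragraph of section 7.3 on additional analyses brings in regression adjustment of the primary and secondary outcomes, but conditionally: "If differences are observed in baseline demographic and/or clinical variables prognostic of outcome". It names neither baseline HOMA nor centre. It leaves subgroup and missing-data details to the SAP; it does not leave the choice of primary test to it.

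Baseline HOMA is planned for all patients. A footnote to the participant timeline, printed under section 5.6, reads: "The baseline HOMA to be done on either of these 2 visits as long as the patient is fasted".

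Section 5.6 sizes the trial for one of the two tests only: "Twenty patients in each group are needed based on 80% power for a two-sample t-test". Its inputs are a 15% difference between arms in the POD 1 change, an SD of 16%, a two-sided level of 0.05 and 10% attrition.

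**The concern.** The two candidate tests answer different questions. The t-test addresses the mean difference that section 7.3 names. Mann-Whitney compares the two distributions by rank, and gives neither a mean difference nor anything to set directly against the 15% in section 5.6. What the primary result means is therefore settled only once the outcome distribution has been seen, from a skewness estimate that is imprecise at about 20 per arm and is held against no stated limit.

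The adjustment rule adds a second data-dependent step: whether the primary model has covariates, and which, depends on imbalance seen after randomisation. Only patients are blinded (sections 4.3 and 6.2), and the research team knows the allocation (section 5.3). Section 6.2 relies on the endpoint being objective. That protects the measurement, not the choice of analysis.

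There is also a possible loss of precision. A change score forces the coefficient on baseline to be exactly 1. ANCOVA estimates it, from data that the trial already collects.

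**Working it through.** **1. The protocol's sample size.** Inputs from section 5.6: difference 15, SD 16, two-sided 0.05, power 80%, attrition 10%.

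n = 2 × (1.960 + 0.842)² × (16/15)² = 17.9, so 18 per arm; 18/0.9 = 20. The stated 20 per group reproduces. With 18 evaluable per arm the exact t-test power is 78.0% (80.3% by the normal approximation).

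**2. Change score against ANCOVA.** Let s0 and s1 be the SDs at baseline and POD 1, k = s1/s0, and rho their correlation.

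- Variance of the change score: s0² + s1² − 2·rho·s0·s1
- Residual variance in ANCOVA: s1²(1 − rho²)
- Difference: (s0 − rho·s1)², never negative and zero when rho·k = 1
- Ratio, ANCOVA to change score: k²(1 − rho²)/(1 + k² − 2·rho·k), which is (1 + rho)/2 when k = 1

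The protocol gives neither rho nor k, so both are assumptions. One reason to look beyond k = 1 is section 4.1, which puts the postoperative fall in insulin sensitivity at about 50%. Since resistance is 100/sensitivity, it would roughly double (1/0.5 = 2), and if spread grows with level, k approaches 2 on the raw scale.

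Taking 16 as the change-score SD, the effective SD is 16 × √ratio. Variance ratio and t-test power at 18 per arm:

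| rho | k = 1 | k = 1.5 | k = 2 |
|---|---|---|---|
| 0.3 | 0.65, 92% | 0.87, 83% | 0.96, 80% |
| 0.5 | 0.75, 88% | 0.96, 79% | 1.00, 78% |
| 0.7 | 0.85, 84% | 1.00, 78% | 0.93, 81% |

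The comparator is 78%. The one degree of freedom spent on baseline is ignored.

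**3. How the skewness rule behaves.** This is an illustrative simulation with all settings assumed: log-normal HOMA with log-scale SD 0.5 at both times, 18 per arm, rho 0.3 to 0.7, change taken as absolute or as a percentage, Mann-Whitney used when |skewness| exceeds 1, an arm effect of 0 or −0.4 on the log scale, and 4,000 runs per setting.

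- Mann-Whitney was selected in about 27 to 71% of trials.
- The two tests disagreed on significance in about 3% of trials under the null and 7 to 13% under an effect.
- Type I error was 4.8 to 6.0% for the skewness rule, against 4.4 to 5.3% for the t-test alone. The Monte Carlo standard error near 5% is √(0.05 × 0.95/4000) = 0.3 percentage points.
- Power of the skewness rule against ANCOVA on log HOMA: 48–55% v 66–67% (rho 0.3), 63–69% v 76–77% (rho 0.5), 84–86% v 89–90% (rho 0.7). These settings favour the log model, because the data are log-normal with equal log-scale SDs.

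**4. Why the log scale suits this endpoint.** Since resistance = 100/sensitivity, ln(resistance) = ln(100) − ln(sensitivity). On that scale the two indices differ only in sign, so the result does not depend on which is reported. That is not true of mean changes on the raw scale.

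**The case against.** The strongest reply is that this is a 40-patient pilot whose rule is declared in advance, that a change score is unbiased in a randomised trial, and that the skewness criterion and covariates may be in an SAP that is not shown. Much of that stands. But an SAP threshold would not repair the mismatch between a named mean difference and a rank test, and section 7.3 does not hand that choice to the SAP.

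Several stronger readings are tempting, and the protocol does not support them:

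- *Baseline HOMA is thrown away.* It is not: the change score uses it by subtraction. It is only missing as a pre-specified covariate.
- *The analysis is simply unadjusted.* Section 7.3 does allow regression adjustment. The fault is that observed imbalance triggers it.
- *False positives are materially inflated.* The simulated inflation is small. Reporting whichever test is more favourable would do more harm, but the protocol selects on skewness, not on the p-value.
- *ANCOVA would bring power to about 90%.* That needs similar SDs at the two times and a low to moderate correlation. In the k = 1.5 and k = 2 columns the gain is between nil and about 5 points.
- *Differing laboratories make centre adjustment essential.* The HOMA appendix says that both sites use the same insulin kit and that the glucose methods agree on average within 2.5%. Within-patient change also removes a constant site offset.

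**Conclusion.** The point holds in a limited form and should be fixed; it does not invalidate the design. Section 7.3 names one quantity and permits a test that does not address it, with no rule precise enough for two analysts to be sure of making the same choice. It then leaves covariate adjustment to the data as well. The sample size is not in error, and no bias in the treatment comparison is shown.

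The main cost is an unstable estimand and room for discretion. The precision cost lies between nil and moderate: from 78%, power would become 78 to 92% over rho 0.3 to 0.7 and SD ratios 1 to 2, all of which are assumed. These figures use the 15% and 16% of section 5.6 as they stand, and so do not describe a log-scale analysis. A purely multiplicative rise would leave the log-scale SD unchanged (k near 1), but the protocol gives no log-scale SD from which to compute that gain.

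**What to change.** In section 7.3, name one primary analysis before any outcome data are seen: ANCOVA of POD 1 HOMA resistance on allocated arm and baseline HOMA resistance. Preferably take logs of both and report a ratio of geometric means with its 95% confidence interval. Use the same model for POD 2 and POD 3, and keep the rank test as a sensitivity analysis only. For the primary outcome, replace the imbalance-triggered adjustment with this pre-specified covariate. Centre is an optional further covariate.

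The change needs no new data. It costs one degree of freedom for baseline and one more if centre is included. It is not quite wording alone: if the log scale is adopted, the outcome definition in section 5.4 and the 15% difference and 16% SD in section 5.6 have to be restated on that scale.

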The rationale for this pilot study is that HPMS drinks given pre-operatively may result in a further reduction in insulin resistance post-operatively compared with standard maltodextrin containing carbohydrate drinks due to a longer duration of action, a greater reduction in peak glucose concentration, a greater reduction in post-operative blood insulin levels and a greater lipid oxidation. This in turn may lead may lead to a greater reduction muscle loss and morbidity, specifically infectious complications, and in turn time to fitness for hospital discharge.

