## 4.3 TRIAL DESIGN

3

Randomised controlled single-blinded (subject only) parallel group, 1:1 allocation ratio superiority framework study.

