#### **SECONDARY OUTCOMES**

- Change in insulin resistance from baseline on POD 2 and POD 3 measured using a technique called HOMA, which utilises serial fasting blood glucose and insulin measurements.
- Stress response following surgery, measured by sampling cortisol levels preoperatively, at the end of surgery, and at 24 hours post-operatively and the inflammatory response measured by CRP levels preoperatively, and on POD 1,2 and 3.
- Ultrasound measurement of gastric volume pre-operatively (see Appendices for technique)
- Recovery profile including:
  - PQRS (see Appendices) score measured pre-operatively, at 2 hours after surgery, POD 3 and POD 7;
  - Muscle strength measured using a grip strength dynamometer pre-operatively, twice daily (morning and afternoon) on POD 1, 2 and 3, and then once daily on alternate days thereafter until discharge (the patient's dominant hand will be used for this measurement, and the best out of three consecutive strengths will be used with mean values analysed);
  - Time to surgical fitness for discharge (see Appendices for criteria) measured in hours (date and time of fitness for surgical discharge is recorded in the ERP database).
- Morbidity measured using the POMS score on POD 2 and POD 5 (see Appendices).
- PONV VAS score on POD 1.
- Sensations of thirst & hunger VAS score immediately pre-operatively and on POD 1.
- Caloric intake POD 1 and 2.
- Ambulation time POD 1 and 2.
- Adverse events i.e. aspiration and hypo- or hyperglycaemia (these are the only relevant safety assessments for these interventions) will be assessed on the operative day for the former & up to the end of POD 1 for the latter.
- Cost analysis: difference in cost between doses of Pre-Load & Generation UCAN and costs of respective hospital and critical care lengths of stay.

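### HOMA is repeated on POD 1, 2 and 3, but section 7.3 tests the days separately, so it does not use a patient's other days when one is missing and estimates neither the average effect nor its change over days

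*Protocol*

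**What the plan says.** Protocol section 5.4 defines the primary outcome as "Change in insulin resistance from baseline on POD 1 measured using a technique called HOMA" and lists as a secondary outcome "Change in insulin resistance from baseline on POD 2 and POD 3 measured using a technique called HOMA". Section 7.1 (post-operative data collection) confirms that the same patients are sampled each day: insulin in triplicate "and glucose on the morning of POD 1, 2 and 3".

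Section 7.3 compares the POD 1 change by an independent-samples t-test or a Mann-Whitney test, depending on skewness. It applies the same choice to "Between-group comparisons of quantitative secondary outcomes including change of insulin resistance from baseline to POD 3". POD 2 is not named there, but as a quantitative secondary outcome it falls under that sentence.

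On missing values, section 7.3 states: "The primary analysis will be based only on data obtained". It promises a missing-data sensitivity analysis, with details in the SAP. Regression is foreseen only where baseline imbalance is seen. The protocol names no repeated-measures analysis.

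**The concern.** Three measurements on one patient are handled as three unrelated data sets. This has two consequences.

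- **Missing days.** A patient whose POD 1 insulin is lost leaves the primary comparison even if POD 2 and POD 3 were measured. The same holds for POD 2 and POD 3. Some loss is foreseeable: section 5.6 allows 10% attrition, section 9.3 keeps data up to withdrawal, and the HOMA appendix sets a 30-minute limit to the laboratory and warns that haemolysis degrades insulin. If absence on POD 3 depends on earlier values, for instance because faster recoverers have gone home, a comparison of those who remain can be biased. A likelihood-based model that uses the earlier days limits this when they explain the absence.
- **Unanswered question.** Separate tests estimate neither the average effect over the three days nor a difference between days. Significance on one day and not on another is not evidence that the effect changed. Yet the HOMA appendix expects the tissue source of insulin resistance to shift by the third day and intends to read the results by timing.

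**Working it through.** **Inputs.** From section 5.6: difference 15, SD 16, two-sided 5% level, 80% power, 10% attrition, 20 per arm. Assumed, because the protocol gives no figure: correlation ρ between days of 0.4 to 0.8, equal for all pairs of days, and SD 16 on each day.

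**1. The plan's own figure.** By the normal formula, n per arm = 2 × (1.960 + 0.842)² × 16² / 15² = 17.9, so 18; 18 / 0.9 = 20. The stated 20 per arm reproduces. With 18 evaluable per arm, the exact t-test power on a single day is 78%.

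**2. Complete POD 1 data.** With 20 per arm the standard error of the POD 1 difference is √(2 × 256 / 20) = 5.06. A model with a separate arm effect on each day also gives 5.06 when every POD 1 value is present, so there is no gain.

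**3. Some POD 1 values missing, POD 2 and POD 3 known.** With the covariance treated as known, the share of POD 1 variance explained by the other two days is R² = 2ρ² / (1 + ρ). If m of n per arm are missing, the variance falls by the fraction R² × m/n relative to the test on observed POD 1 values only.

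| ρ | R² | 2 of 20 missing | 4 of 20 missing |
|---|---|---|---|
| 0.4 | 0.229 | 2.3% | 4.6% |
| 0.6 | 0.450 | 4.5% | 9.0% |
| 0.8 | 0.711 | 7.1% | 14.2% |

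In standard-error terms, 2 of 20 missing gives √(2 × 256 / 18) = 5.33 for the separate test, against 5.27 to 5.14 with the model. A simulation that estimated the covariance gave slightly smaller variance savings: about 2-5% and 4-12%. By symmetry the known-covariance formula applies equally to POD 3 when POD 1 and POD 2 are known.

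**4. The POD 1-3 average, as an illustration.** Assume a constant effect of 15 on all three days. The variance of a patient's three-day mean is 256 × (1 + 2ρ) / 3.

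| ρ | SD of mean | Power, 18 per arm |
|---|---|---|
| 0.4 | 12.4 | 94% |
| 0.6 | 13.7 | 89% |
| 0.8 | 14.9 | 84% |

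A single day has 78%. The average is a different, secondary quantity, so this is not a gain for the primary comparison.

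**5. Discordance and multiplicity, for context.** Under the same constant effect, simulation shows the three day-wise tests disagreeing on significance in about 40%, 33% and 23% of trials at ρ = 0.4, 0.6 and 0.8. With no effect, at least one of the three is significant in about 13%, 12% and 10%. With complete data, a model with arm-by-day terms and unstructured covariance, before baseline adjustment, returns the same day-specific mean differences, so the model does not cure either.

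**The case against.** The strongest reply is that the planned primary analysis is sound. There is one primary day, the sample size is built for that exact test, and with 10% missing the saving is only about 1-4% in standard error. All of this stands.

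Four stronger readings are tempting, and the document does not support them.

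- **That separate tests inflate the trial's type I error.** The 10-13% concerns the set of three HOMA results. POD 2 and POD 3 are secondary, and the primary test keeps its 5%.
- **That a mixed model would stop the days disagreeing.** Day-specific contrasts from it can still differ in significance.
- **That the rationale requires a duration analysis.** The phrase "due to a longer duration of action" in section 4.1 describes the drink's glucose profile, as the account of the starch trials earlier in that section shows. It is not a hypothesis about persistence over POD 1-3.
- **That power rises from 78% to as much as 94%.** That figure belongs to an average the protocol does not define, under a constant effect that the HOMA appendix makes doubtful.

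It is also fair that a patient is lost only from the missing day, that a missing-data sensitivity analysis is promised, and that early-discharge bias on POD 3 rests on an assumed mechanism. In one simulation with 10% missing, the POD 3 difference fell by about 0.4 points, against a standard error of 5.3.

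The reply that this is all SAP content does not stand: section 7.3 itself names the tests, and a SAP that followed it would carry the limitation over.

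**Conclusion.** The point holds as a modest, inexpensive improvement. It is not a fault in the primary test. The separate tests leave known values unused for partly observed patients, give no protection if POD 3 absence depends on earlier days, and yield no direct estimate of the average effect or of its change over days.

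The gain in POD 1 variance is nil with complete data, about 2-7% with 2 of 20 per arm missing and about 5-14% with 4 of 20. These figures rest on an assumed equal correlation of 0.4 to 0.8, a known covariance, and patients with a missing POD 1 value having both later days. The 4 of 20 case goes beyond the protocol's 10% allowance. The larger power figures illustrate a secondary quantity only.

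**What to change.** Keep HOMA change from baseline to POD 1 as the primary outcome. In section 7.3:

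1. Replace the separate POD 2 and POD 3 tests with one linear mixed model for repeated measures on POD 1, 2 and 3. The response is HOMA change, or log HOMA with log baseline as covariate; fix the scale in advance, since a change score can be negative and cannot be logged.
2. Include baseline HOMA, arm, day and arm-by-day, with unstructured within-patient covariance and small-sample degrees of freedom.
3. Report POD 2, POD 3, the POD 1-3 average and the arm-by-day term as secondary results.
4. State in advance whether the model's POD 1 contrast is the primary estimate or a supportive analysis for use when POD 1 values are missing.
5. Do not claim that the model removes day-to-day discordance or multiplicity.

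Do not extend this to CRP until its sampling days are reconciled: section 5.4 lists POD 1, 2 and 3, while section 7.1 lists POD 1 and 3.

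The cost is wording in section 7.3 and the SAP and a little analysis time, with no new patients or samples. The downside is reliance on a model and on missing-at-random, which the sensitivity analysis already promised in section 7.3 should examine.

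### By default, section 7.3 makes no use of the preoperative grip strength and PQRS values the trial collects, which costs precision, but not validity, in these secondary comparisons

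*Protocol*

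**What the plan says.** Protocol section 7.3 sets one rule for the quantitative secondary outcomes. It lists the change in insulin resistance to POD 3 and continues: "the PQRS score and time to surgical fitness will made using either the Independent Samples T-Test or Mann-Whitney U Test", with the choice depending on skewness. Insulin resistance is the only outcome there that is expressed relative to baseline.

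Grip strength is not named in 7.3. It comes under the general rule because the listed outcomes are given as examples. Section 5.4 says of the readings that "the best out of three consecutive strengths will be used with mean values analysed", and does not mention change or a covariate.

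Both outcomes have a preoperative value. The preoperative clinic list in section 7.1 includes "Baseline hand grip strength measurement" and "Baseline PQRS score questionnaire", and also baseline cortisol and CRP.

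The paragraph on additional analyses in 7.3 provides for regression adjustment of primary and secondary outcomes if prognostic baseline variables are seen to differ. It does not define a difference or name the outcome's own baseline as a covariate. It leaves subgroup details and missing-data sensitivity analyses to the statistical analysis plan, but not the main test.

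**The concern.** Grip strength can be expected to vary between patients with sex, age and build, and the trial takes adults over 18 of either sex. A comparison of postoperative levels keeps all of that between-patient variation in the error term. It also passes any chance baseline difference, scaled by r, into the estimate this one trial produces.

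Section 4.1 expects the new drink to reduce muscle loss, and grip strength is the protocol's functional measure of muscle. A pilot should estimate such effects as precisely as its data allow. Here the information that would sharpen the estimate is collected and then not used by default.

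**Working it through.** **1. The protocol's own sample size.** Section 5.6 states: "Twenty patients in each group are needed based on 80% power for a two-sample t-test". The inputs it gives are a target difference of 15%, an SD of 16% and a two-sided 5% level, all for the insulin resistance change to POD 1. It adds: "This sample size calculation allows for 10% attrition".

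- Normal approximation: n = 2 × (1.960 + 0.842)² × (16/15)² = 17.9, rounded up to 18 per arm. Then 18/0.9 = 20, which matches.
- The exact t-test needs 19 per arm; its power with 18 completers per arm is 78.0%.
- This calculation covers insulin resistance only. No secondary outcome was used to set the size.

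**2. What 20 per arm gives for an unadjusted secondary comparison.** With the two-sample t-test (noncentral t), two-sided 5% and 80% power, the detectable difference is 0.91 SD. With 18 completers per arm it is 0.96 SD.

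**3. What ANCOVA on baseline would give.** The residual variance is multiplied by 1 − r² and one degree of freedom is lost. The detectable difference is therefore about the unadjusted figure × √(1 − r²); for example, at r = 0.7, 0.91 × √0.51 = 0.65 SD. The equivalent unadjusted size is 20/(1 − r²) per arm. The protocol gives no r, so the values below are assumed. The 0.5 SD effect in the power column is also assumed.

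| Assumed r | 1 − r² | Detectable, 20 per arm | Detectable, 18 per arm | Power for 0.5 SD, 20 per arm | 20 per arm works like |
|---|---|---|---|---|---|
| Unadjusted | 1 | 0.91 SD | 0.96 SD | 34% | 20 |
| 0.3 | 0.91 | 0.87 SD | 0.92 SD | 37% | 22 |
| 0.5 | 0.75 | 0.79 SD | 0.83 SD | 43% | 27 |
| 0.7 | 0.51 | 0.65 SD | 0.69 SD | 58% | 39 |
| 0.9 | 0.19 | 0.40 SD | 0.42 SD | 94% | 105 |

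**4. Why not simply analyse change scores.** Their variance factor is 2(1 − r), so they beat the unadjusted level only when r exceeds 0.5. With 20 per arm the detectable difference is 1.08 SD at r = 0.3, 0.91 SD at 0.5 and 0.70 SD at 0.7. ANCOVA does better at each of these values.

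**5. Chance imbalance and the conditional rule.** The standard error of a baseline difference is √(2/20) = 0.32 SD. An imbalance above 0.3 SD in either direction is therefore expected in about one trial in three. At r = 0.7 it moves the unadjusted estimate by 0.7 × 0.3 = 0.21 SD. Such an imbalance is only 0.3/0.32 ≈ 0.9 standard errors, so a trigger based on statistical significance would not respond to it. The protocol does not say what its trigger is.

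**The case against.** The strongest case against has four parts.

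- **The text is less explicit than the concern needs.** Section 7.3 does not name grip strength. The phrase about mean values in 5.4 may describe only how repeated readings are reduced, and the reference to the PQRS score does not say whether level or change is compared. This stands in part: analysis of the raw level is a reading of the text, not a statement in it. However, the unadjusted test is stated as the general rule, and change from baseline is specified for insulin resistance alone.
- **Such detail may belong to the statistical analysis plan, which is not at hand.** That is fair for the choice of time points and the derivation of scores. It is weaker for the test itself, which the protocol fixes.
- **The conditional adjustment already deals with imbalance.** It does cover secondary outcomes, and baseline grip strength could count as a prognostic clinical variable, so the analysis is unadjusted only by default. But the clause leaves the trigger undefined, makes the model depend on the observed data, and recovers no precision when the arms look alike.
- **These are secondary outcomes of a pilot sized for insulin resistance.** This stands, and it limits the weight of the point.

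A reader might also infer that between-patient variation swamps these outcomes, that a plausible effect on grip strength could not be detected, or that the comparison is biased. The documents support none of these. They give no r, no SD and no plausible effect for grip strength. The unadjusted detectable difference of 0.91 SD is close to the 15/16 = 0.94 SD that the protocol adopts for its primary outcome. Randomisation keeps the unadjusted comparison unbiased over repeated trials.

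**Conclusion.** The point holds as a minor one about precision. The default analysis plans no use of preoperative values that the trial already collects, and the conditional adjustment does not make up for this.

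The size depends on r. At r = 0.3 the gain is slight (0.91 to 0.87 SD). At r = 0.7 it is substantial (0.91 to 0.65 SD, as if there were about 39 per arm). A high r is plausible for repeated readings of the same dominant hand, but it remains an assumption. The documents give no basis for a value of r for PQRS, cortisol or CRP.

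The figures assume a roughly normal outcome, a linear relation to baseline and one postoperative value per patient. They refer to the t-test; if the Mann-Whitney test were chosen they would be only a guide.

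**What to change.** In section 7.3, state that postoperative grip strength at a named time point, or its mean over POD 1 to 3, will be compared between arms by ANCOVA. The patient's preoperative grip strength should be a planned covariate whether or not the baselines look different. Report the adjusted difference with its 95% confidence interval.

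Apply the same to cortisol and CRP at named time points, log-transformed if skewed. For CRP, note that section 5.4 lists POD 1, 2 and 3 while the postoperative list in 7.1 gives only POD 1 and 3. Apply it to PQRS only where a numeric score is defined: Appendix 10.3 lists the items but gives no rule for a total.

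Add a simple rule for a missing preoperative value, such as mean imputation of the covariate.

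The cost is a change of wording and one degree of freedom per model. No visit, measurement or patient is added.
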